18 CONCOMITANT MEDICATIONS/THERAPIES

For the purposes of this clinical study, only medications taken or administered for the following will be recorded *(Ensure medications reflected in incl/excl are listed here)*:

- Muscle relaxation;
- Other medications related to or given for the participant's MDD.

19 Adverse Event & Device Deficiency Reporting

Subjects will be carefully monitored during the study for possible adverse events (AEs) from the time they sign the Informed Consent Form to the time of study completion. All medical events and conditions prior to this time point are to be captured as medical history.

Any observed unanticipated AE will be fully investigated by the Investigator and classified in line with the definitions of ISO 14155:2020 below. The frequency and severity of anticipated AEs will instead be captured using the tDCS Adverse Events Questionnaire (AEQ).

All unanticipated adverse events that occur during this study will be recorded on the adverse event eCRFs and must include the following information at minimum:

- Event Description
- Date of Onset
- Date of Resolution
- Severity
- Seriousness
- Relationship to Study Device/Procedure
- Outcome

Adverse events will be reported and classified by the Investigator using the specific signs, symptoms or abnormal laboratory values, or medical diagnosis if no signs, symptoms, or abnormal laboratory values can be identified.

Significant new information and updates should continue to be captured in the subject's records and in the EDC as they become available and the adverse event should be followed until it is resolved or no further improvement is expected, or the subject is lost to follow-up.

Adverse events that meet the definitions of seriousness in Section 19.1 below should also be reported to the Sponsor per the instructions provided in Section 19.2.4 below.

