19.1 DEFINITIONS

The following definitions are from the ISO 14155:2020 and MDCG 2020-10:

Adverse Event (AE) – An adverse event (AE) is any untoward medical occurrence, unintended disease or injury, or untoward clinical signs (including abnormal laboratory findings.) in subjects, users, or other persons, whether or not related to the investigational device and whether anticipated or unanticipated.

NOTE 1: This definition includes events related to the investigational medical device or the comparator.

NOTE 2: This definition includes events related to the procedures involved.

NOTE 3: For users or other persons, this definition is restricted to events related to the use of investigational medical devices.

Anticipated Adverse Events – Anticipated adverse events are adverse events that have been identified as adverse events related to the investigational device or study procedure. The anticipated events of this clinical investigation are outlined in tDCS Adverse Events Questionnaire (AEQ). The frequency and severity of anticipated AEs will be captured using AEQ.

Anticipated adverse events are:

- Headache
- Neck pain
- Scalp pain
- Tingling
- Itching
- Burning sensation
- Skin redness
- Sleepiness
- Trouble concentrating
- Acute mood change

Adverse Device Effect (ADE) – An adverse device effect (ADE) is any adverse event related to the use of an investigational device. This definition includes:

CONFIDENTIAL Page **50** of **69**

- Adverse events resulting from insufficient or inadequate instructions for use, deployment, implantation, installation, or operation, or any malfunction of the investigational medical device.
- Any event resulting from use error or from intentional misuse of the investigational medical device.
- "Comparator" if the comparator is a medical device.

Serious Adverse Event (SAE) – A Serious Adverse Event is an AE which:

- 1. Led to a death,
- 2. Led to serious deterioration in the health of the subject, users, or other persons that either resulted in:
 - a) A life-threatening illness or injury, or
 - b) A permanent impairment of a body structure or a body function including chronic diseases, or
 - c) In-patient or prolonged hospitalization, or
 - d) Medical or surgical intervention to prevent life threatening illness or injury or permanent impairment to a body structure or a body function.

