19.2.2 Assessment of Relationship to Use of the Investigational Device or Procedure

The relationship between the use of the medical device (including the medical - surgical procedure) or control procedure the occurrence of each unanticipated adverse event shall be assessed and categorized. During causality assessment, clinical judgment shall be used, and the Clinical Protocol shall be consulted, as all the foreseeable adverse events and the potential risks are listed and assessed there. The presence of confounding factors, such as concomitant medication/treatment, the natural history of the underlying disease, other concurrent illness or risk factors shall also be considered.

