22.14 SAFETY ANALYSES

Assessment of the safety of the investigational device will include an evaluation of the incidence and severity of complications and adverse reactions associated with the treatment.

Adverse event rates will be summarized by type of AE and for specific AEs in two ways:

- 1. per subject incidence of specific AEs and classes of AEs and
- 2. by event, summarizing event counts by visit interval over time and in accordance with FDA Guidance (CDRH 2004)¹⁵.

Device and procedure-related events will be summarized by severity and relatedness. Events listings that include details such as relatedness, severity, onset, and resolution status will be provided for all events and relevant subsets of events such as serious events and related events. Primary safety comparisons will be performed using the AT analysis set. The summary tables will show the adverse events (in coded terms), the total number of events, and the number and the percentage of subjects affected in each treatment group

¹⁵ CDRH. Guidance for Industry and FDA Staff: Clinical Data Presentations for Orthopedic Device Applications, December 2, 2004.

("subject wise evaluation") and stratified by relation to device and severity. Data of dropouts will be presented separately, and possible bias will be discussed in the final report.

All AEs will be summarized in listings for the AT analysis set. The following AE listings will be constructed:

- AE Listing 1 All AEs Sorted by Group and Event Type
- AE Listing 2 All AEs Sorted by Group and Subject
- AE Listing 3 Serious AEs
- AE Listing 4 Severe AEs
- AE Listing 5 Device Related AEs
- AE Listing 6 Serious Device Related AEs
- AE Listing 7 Severe Device Related AEs
- AE Listing 8 Other AEs
- AE Listing 9 AEs among subjects discontinued early
- AE Listing 10 AEs among subjects who died

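### Section 19 sends anticipated adverse events to the AEQ, but the visit, monitoring, adjudication and analysis sections cover all adverse events, so common non-serious device effects may be missing or unevenly recorded in the safety tables

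*Protocol*

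**What the plan says.** **Collection.** Section 19.1 defines the class: "Anticipated adverse events are adverse events that have been identified as adverse events related to the investigational device or study procedure". It lists ten event types, among them headache, tingling, itching, burning sensation and skin redness. Section 19 then splits the recording. For the anticipated class, "The frequency and severity of anticipated AEs will instead be captured using the tDCS Adverse Events Questionnaire (AEQ"). For the rest, "All unanticipated adverse events that occur during this study will be recorded on the adverse event eCRFs", with a minimum set of fields that includes onset, resolution, relationship and outcome. Section 19.2.2 follows the same split: "the occurrence of each unanticipated adverse event shall be assessed and categorized". Section 19.2.4 brings serious events back in, whether anticipated or not.

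**Text without the split.** The visit lists in 13.2 to 13.5 have staff record adverse events generally. A further sentence of Section 19 has the investigator report and classify adverse events with no restriction to unanticipated ones. Section 21.2 has monitors verify that all of them reach the sponsor.

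**Outputs.** Section 22.14 promises a summary "by event, summarizing event counts by visit interval over time". It adds "Device and procedure-related events will be summarized by severity and relatedness" and "Events listings that include details such as relatedness, severity, onset, and resolution status will be provided for all events". The named listings include two of all AEs and "AE Listing 5 Device Related AEs". Section 19.4 opens by having the events committee adjudicate every AE.

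**The AEQ itself.** Table 1 schedules it at Week 10, Week 20 and early termination. Section 22.9 places it among the exploratory endpoints, as a continuous summary in the mITT population. Section 22.3.2 assigns all safety and tolerability summaries to the AT set.

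**The concern.** The analysis section promises outputs that need data which the collection rules do not require. The events affected are the ones that the protocol itself identifies as device or procedure effects. A reader of the all-AE and device-related tables would expect to find them there.

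If sites follow Section 19 literally, the device-related tables may show few or no non-serious headaches or burning sensations, and known device effects would look rarer than they are. If one site follows Section 19 and the other follows the visit lists, adverse event rates by country would differ because of recording practice. There are only two sites, one in each country, so the two causes could not be separated.

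This cannot be left to the SAP. What is recorded, when and with which fields is fixed in the protocol, and an analysis plan cannot recover a date or a relationship judgment that was not collected. The results are intended to support a premarket application (24.4).

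**Working it through.** No figure in the plan is at issue, so the check sets the collection rules beside the promised outputs.

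| Output | What it needs | Required for a non-serious anticipated AE? |
|---|---|---|
| Counts by visit interval (22.14) | an event date, or capture at each visit | Not by Section 19; general wording in 13.2 to 13.5 |
| Summary by severity and relatedness (22.14) | severity and a relationship grade | Severity through the AEQ; no grade under 19.2.2 |
| Listings with onset and resolution (22.14) | two dates | No |
| Device-related listing (22.14) | an eCRF record identified as related | No eCRF record required by Section 19 |
| Adjudication (19.4) | a reported event; for the narrower review, a relationship grade | Not by Section 19 or 19.2.2 |

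**The second sentence of 19.4.** It narrows review to SAEs, events judged related or of unknown relationship, and some others. This does not remove the conflict. Either anticipated types count as related because 19.1 defines them so, and they fall under the review, or each needs a relationship grade that 19.2.2 does not ask for.

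**Timing, from Table 1.** Blinded-phase adverse event reviews take place at Weeks 0, 1, 4, 7 and 10, which is 5. The AEQ is scheduled at Week 10 only, which is 1. The intervals after Week 0 end at Weeks 1, 4, 7 and 10, which is 4. A single questionnaire at Week 10 cannot give separate counts for the first 3 of these (4 − 1 = 3). The early termination visit in 15.4 is optional and does not change this.

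**Overlap with known effects.** Of the four entries in Table 4 (9.1), headache is on the 19.1 list in full. Two entries match in part: redness is listed but skin irritation is not, and tingling and itching are listed but stinging is not. Increased tinnitus is not listed. So 1 matches fully, 2 partly and 1 not at all (1 + 2 + 1 = 4).

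**Analysis set.** Both mITT (22.3.3) and AT (22.3.2) require at least one treatment. They differ in that mITT drops subjects randomized in error and analyses by randomized arm, while AT analyses by treatment received. The protocol expects few mITT exclusions. The numerical effect is therefore probably small, but 22.9 and 22.3.2 still give different rules for the AEQ.

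**Baseline.** Section 13.1 lists the AEQ among the screening assessments. Table 1 does not schedule it there.

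**The case against.** The best defence is that nothing forbids entering an anticipated AE on the eCRF. The definition in 19.1 covers anticipated events, the visit lists call for recording adverse events at every visit, a sentence in Section 19 has the investigator classify them, and 21.2 has monitors check that they are reported. A careful site could record all of them with dates. This stands, and it limits the point to events that may be missing, incomplete or uneven. It does not settle the matter, because Section 19 is the specific rule, uses the word *instead*, and sets the minimum fields for unanticipated events only.

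A second defence is that the effects are not lost. Serious ones are reported under 19.2.4, AEQ responses go into the EDC under 24.2, and AEQ results are planned at Weeks 10 and 20. Section 22.3.2 can be read as covering the AEQ too. All of this is right. What remains is that 22.14 does not mention the AEQ, and 22.9 gives it an exploratory role under a different analysis set.

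Third, the routing is deliberate: the revision history for version 6 says so. Most people get transient skin redness (9.1), so logging every sensation would burden sites and the committee. That is a sound reason for the AEQ route, which is not challenged here.

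Finally, the AEQ form is not shown. It may ask about relationship. The protocol assigns it only frequency and severity.

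**Conclusion.** The point holds as an internal inconsistency that should be corrected. Section 19 and 19.2.2 limit eCRF recording and causality assessment to unanticipated events, while 13.2 to 13.5, 19.4, 21.2 and 22.14 are written for all events. As a result, non-serious anticipated effects may be absent, incomplete or recorded differently between the two sites in the all-AE and device-related tables and listings. The one scheduled blinded-phase AEQ cannot fill the intervals ending at Weeks 1, 4 and 7.

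A reader might infer two stronger conclusions that the documents do not support:

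- That these events are certain to be missing. The general recording instructions rule that out.
- That three of the four common effects in Table 4 could not reach the device-related listing. Only headache matches the anticipated list in full; skin irritation, stinging and tinnitus are not on it and could be entered as unanticipated.

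No size of bias is claimed, since the documents give no basis for one. The conclusion assumes that Section 19, as the specific rule, guides at least some recording, and that the AEQ supplies only the frequency and severity that the protocol assigns to it.

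**What to change.** 1. Reconcile 13.2 to 13.5, 19, 19.2.2, 19.4, 21.2 and 22.14 on which adverse events are entered on the eCRF, so that both sites follow one rule.
2. If the AEQ route is kept, state in 22.14 and 19.4 that the date, interval, relatedness and adjudication outputs cover only events recorded on the eCRF, and that non-serious anticipated effects are reported from the AEQ.
3. In that case, add to 22.14 an AEQ table of per-subject incidence and severity by arm at Week 10, with early termination AEQs, in the AT set. Align 22.9 with 22.3.2.
4. Reconcile 13.1 with Table 1 on whether a baseline AEQ is taken.

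If the AEQ route is kept, the cost is text edits and one table from data already planned, plus whatever step 4 settles about the baseline form. No new visit or staff is needed. Entering every transient sensation on the eCRF is not asked for.

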19.2.3 SAE RELATIONSHIP ASSESSMENT

Per MDCG 2020-10/1 (May 2020), Investigators will assess the potential relationship of the SAE to the use of the investigational device (including the surgical procedure) or control procedure and classify the causality of the event according to the following definitions.

- **Not Related**: Relationship to the device or procedures can be excluded when:
 - the event has no temporal relationship with the use of the investigational device, or the procedures related to application of the investigational device;
 - the serious event does not follow a known response pattern to the medical device (if the response pattern is previously known) and is biologically implausible;
 - the discontinuation of medical device application or the reduction of the level of activation/exposure - when clinically feasible - and reintroduction of its use (or increase of the level of activation/exposure), do not impact on the serious adverse event;
 - the event involves a body-site or an organ that cannot be affected by the device or procedure;
 - the serious event can be attributed to another cause (e.g., an underlying or concurrent illness/ clinical condition, an effect of another device, drug, treatment, or other risk factors);
 - the event does not depend on a false result given by the investigational device used for diagnosis, when applicable;
 - harms to the subject are not clearly due to use error;
 - In order to establish the non-relatedness, not all the criteria listed above might be met at the same time, depending on the type of device/procedures and the serious adverse event.
- **Possible:** The relationship with the use of the investigational device or the relationship with the procedure is weak but cannot be ruled out completely. Alternative causes are also possible (e.g., an underlying or concurrent illness/ clinical condition or/and an effect of another device, drug, or treatment). Cases where relatedness cannot be assessed or no information has been obtained should also be classified as possible.
- **Probable**: The relationship with the use of the investigational device or the relationship with the procedure, seems relevant and/or the event cannot reasonably be explained by another cause.
- **Causal Relationship**: The serious adverse event is associated with the investigational device or with procedures beyond reasonable doubt when:

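### Section 19 allows an adverse event to be classified by diagnosis only when no sign, symptom or laboratory value can be identified, so a diagnosed condition can be fragmented or hidden in the safety tables, or reduced to anticipated symptoms that bypass the adverse event eCRF

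*Protocol*

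**What the plan says.** Section 19 of the protocol (Adverse Event & Device Deficiency Reporting) sets the reporting rule in one sentence. It begins "Adverse events will be reported and classified by the Investigator using the specific signs, symptoms or abnormal laboratory values" and continues "or medical diagnosis if no signs, symptoms, or abnormal laboratory values can be identified". Signs, symptoms and laboratory values come first, and a diagnosis is the fallback.

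The same section divides events between two routes. "All unanticipated adverse events that occur during this study will be recorded on the adverse event eCRFs", with at least a description, onset, resolution, severity, seriousness, relationship and outcome. For anticipated events, frequency and severity are captured by the AEQ instead.

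Section 19.1 defines an adverse event as "any untoward medical occurrence, unintended disease or injury, or untoward clinical signs". It also says "Anticipated adverse events are adverse events that have been identified as adverse events related to the investigational device or study procedure" and lists ten of them: headache, neck pain, scalp pain, tingling, itching, burning sensation, skin redness, sleepiness, trouble concentrating and acute mood change.

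Section 22.14 summarises adverse events in two ways: "per subject incidence of specific AEs and classes of AEs and" then "by event, summarizing event counts by visit interval over time". Its by-group tables show coded terms, total events, and the number and percentage of participants affected.

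**The concern.** Most illnesses that can be diagnosed have at least one sign or symptom. If a diagnosis may be used only when there is none, it will seldom qualify, even when the investigator has made it with confidence. The safety tables are built from the reported terms, so a term that sites were told not to use cannot appear in them.

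Two things are at stake. The first is whether the comparison of arms in Section 22.14 shows the conditions that occurred or only their component symptoms. The second is routing. The anticipated list consists almost entirely of symptom-level terms, so describing an unlisted condition by its symptoms can change it from an unanticipated event to an anticipated one. It then loses the eCRF record and the relationship assessment that Section 19.2.2 requires for unanticipated events.

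**Working it through.** The protocol gives no figure to reproduce and no formula applies. The check sets the sections side by side.

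1. **Order of the rule.** Section 19 makes the absence of any sign, symptom or laboratory value the condition for using a diagnosis. This is a stated rule, not an omission that the SAP might fill.

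2. **Definition.** Section 19.1 counts disease and injury as adverse events alongside clinical signs. A disease can therefore be an adverse event by definition and yet, under Section 19, not be reportable under its own name if it has a symptom.

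3. **Effect on the tables.** Take one participant with one diagnosed illness that has k symptoms. The wording of Section 19 fits two readings.
   - One record, classified by a symptom: event count 1, count for the diagnosis 0, participants with any event 1.
   - One record per symptom: event count k, count for the diagnosis 0, participants with any event 1. If k is assumed to be 2 to 4, one illness becomes 2 to 4 events.

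   Under literal compliance the diagnosis is missing from the coded terms on either reading. Only the second raises the event count. Neither changes the number of participants with any event.

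4. **Effect on routing.** Section 9.1 names small skin burns as a risk known from the literature. A burn is not among the ten anticipated events in Section 19.1; burning sensation and skin redness are.
   - Reported as a burn: unanticipated, so recorded on the adverse event eCRF with onset, seriousness and relationship.
   - Reported as burning sensation plus skin redness: both terms anticipated, so captured by the AEQ for frequency and severity. In Table 1 the AEQ falls at week 10, week 20 and early termination only, with none at weeks 1, 4 and 7.

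   The same burn therefore leaves a different record depending only on how it is named.

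5. **Search for a rule that recombines symptoms.** Section 19.4 has the Clinical Events Committee adjudicate all adverse events, and Section 22.14 adds classes of events and a listing sorted by participant. None of these tells anyone to merge symptoms into a diagnosis.

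**The case against.** The strongest reply is that the sentence is awkward but the consequences are inferred. Much of this stands.

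- **No text orders one record per symptom.** Each event has a free description, and nothing forbids naming the diagnosis there. A reader might infer that event counts are inflated several-fold. The protocol does not support that: the multiplier is an assumption, and for listed symptoms the effect is mostly a move to the AEQ, which would not raise eCRF counts.
- **No standard error is at risk.** A reader might infer that correlated symptoms make event-rate standard errors too small. Section 22.14 specifies counts, percentages and listings, with no event-rate standard error.
- **Causality.** The question in Section 19.2.3 of whether "the serious event does not follow a known response pattern to the medical device" concerns serious events only. Other unanticipated events fall under Section 19.2.2, which asks for clinical judgment, including concurrent illness. A reader should not infer that causality assessment fails generally.
- **Missed syndromes.** A reader might infer that a real device-related syndrome would go unseen. That is too strong. Serious events, anticipated or not, are reported within 24 hours (Section 19.2.4). Mania is tracked with the YMRS at follow-up visits (Section 9.1). A burn is a visible lesion that an investigator could report as a sign. The chance that a rare syndrome occurs at all in an arm does not depend on this rule.
- **Scope.** Many known effects of the device are symptoms without a diagnosis, and for these the rule changes nothing. The eCRF guide and coding conventions are not shown.

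What does not stand is the suggestion that these safeguards repair the rule. Adjudication, listings by participant and class-level summaries can reveal a cluster of symptoms, but none is required to restore the diagnosis. An analysis plan cannot recover a term that was never collected.

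**Conclusion.** The concern holds as a defect in the reporting rule. Section 19 puts diagnosis last, which sits badly with the definition in Section 19.1. Followed as written, it can fragment or hide a diagnosed condition in the coded-term tables of Section 22.14, and it can reduce an unlisted condition to anticipated symptoms that go to the AEQ.

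The size cannot be computed from the protocol, because it depends on how literally sites apply the sentence, how many symptoms each condition has, and coding rules that are not shown. The effect falls mainly on non-serious conditions that have a diagnosis. The share of participants with any adverse event, counting both routes, is unaffected, and so is the primary endpoint. The conclusion assumes that sites follow the sentence as written and that no unseen instruction reverses it.

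**What to change.** Reverse the order in Section 19. When the investigator can make a diagnosis, report it as one adverse event, with its signs and symptoms recorded as descriptors. Report signs, symptoms or laboratory values as events only when no unifying diagnosis is available. Add that whether an event is anticipated is decided from the diagnosis where there is one, not from its component symptoms.

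The cost is one sentence in Section 19, the added statement on anticipated status, and a matching line in the eCRF completion guide. No new data are needed. The small downside is that investigators must judge whether a diagnosis can be made.
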